1.2 Idiopathic Inflammatory Myopathies

Idiopathic inflammatory myopathies (IIMs) are a heterogeneous group of acquired, systemic connective tissue diseases characterized by chronic inflammation of striated muscles leading to predominantly proximal muscle weakness. They are best classified on the basis of their varying clinical characteristics into the most common subsets of IIM: adult dermatomyositis (DM) and polymyositis (PM), juvenile DM, necrotizing autoimmune myositis, myositis in overlap with cancer or another connective tissue disease, and inclusion body myositis.[1] IIMs are frequently associated with constitutional symptoms and commonly involve other organ systems including the skin, joints, lungs, gastrointestinal tract and heart. Patients with IIM have increasing difficulty with tasks requiring the use of proximal muscles, such as getting up from a chair, climbing steps, or lifting objects. In rare acute cases also respiratory muscles can be affected. Extra-muscular disease activity may manifest in systemic symptoms like fever, arthralgia, and Raynaud's phenomenon, cardiac arrhythmias or ventricular dysfunction, and pulmonary complications, primarily due to interstitial lung disease (reported in 10-40% of patients).[1]

IIMs are rare with an estimated incidence of 4-10 cases/million population per year, and a bimodal incidence pattern reflecting childhood onset of juvenile DM and a later peak in adulthood.[2]

Each IIM subtype has a different prognosis and response to therapies so that the distinction from other diseases is very important. Although the precise pathogenesis is unknown, the IIMs likely result from immune-mediated processes initiated by environmental factors in genetically susceptible individuals.[3]

Although a spectrum of severity exists for DM, this entity is more likely to be associated with rapid and aggressive myositis. DM is seen in both, children and adults, and the early symptoms include distinct skin manifestations accompanying or preceding muscle

weakness. The classic skin manifestations include periorbital heliotrope (blue-purple) rash with edema; erythematous rash on the face, knees, elbows, malleoli, neck, anterior chest (in a V-sign), and back and shoulders (in a shawl sign); and a violaceous eruption (Gottron's rash) on the knuckles, which may evolve into a scaling discoloration. The lesions are photosensitive and may be aggravated by ultraviolet radiation.

The risk of cancer is increased in adults during the first 3-5 years after the onset of DM, with a reported frequency of 9-32%; necessitating a thorough annual workup in the first 3 years after disease onset. The most common forms are ovarian, breast, and colon cancer, melanoma, and non-Hodgkin's lymphoma.

1.3 Rationale for Conducting the Study

In addition to its use for the treatment of primary and secondary immunodeficiencies, IGIV is increasingly used for immunomodulating therapy in the treatment of patients with a variety of autoimmune and inflammatory neurological disorders. However, there is only 1 placebo-controlled clinical study in 15 subjects with refractory DM published so far, employing a dose of 2.0 g/kg IGIV or placebo for 12 weeks. After a 1-month washout phase the subjects crossed over to the alternate therapy. [4] Subjects on IGIV had a significant improvement in muscle strength and neuromuscular symptoms in contrast to subjects on placebo. A total of 12 subjects received IGIV of which 9 subjects had a major improvement to nearly normal function.

The rationale for conducting this study (ProDERM: "Progress in DERMatomyositis") is to investigate efficacy, safety and tolerability of Octagam 10% in DM patients and to confirm the efficacy results, which were observed in the small randomized placebo-controlled cross-over trial [4] and also seen in retrospective studies or case reports, in a much larger setting. Furthermore, ProDERM will systematically investigate the long-term beneficial effect of IGIV in a 6-month open-label extension period. Long-term safety and tolerability of high-dose Octagam 10% (2.0 g/kg) administered for up to 40 weeks will be investigated, since many patients need lifelong treatment. Eventually, Octagam 10% should offer DM patients an additional effective and safe maintenance treatment option that is well tolerated.

1.4 Dose Rationale

In 1989, Imbach and colleagues published a randomized placebo-controlled trial in which IGIV at a dose of 2.0 g/kg has been used for the first time in an immunomodulatory setting in immune thrombocytopenia. [5] Later retrospective and case studies relied mostly to this dosage scheme and the effect of IGIV has never been systematically examined in another randomized placebo-controlled trial since.

Subjects with mild to moderate DM may respond to lower doses of IGIV. Therefore, and following a recommendation of the FDA, subjects may receive the lower 1.0 g/kg Octagam 10% dose from Week 28 on, depending on the investigator's decision and if the higher dose has shown to be effective in the individual subject. An Advisory Board of DM experts in the fields of neurology, rheumatology and immunology confirmed this observation. Reference is also made to a group of investigators in Italy who successfully treat their patients with weekly (subcutaneous) doses of only 0.1-0.2 g/kg, corresponding to a monthly (intravenous) dose of 0.8 g/kg.[31]

1.5 Benefit-Risk Statement

The risks of IGIV administration are well documented. In general, the incidence of adverse events (AEs) associated with IGIV tends to increase with the rate of infusion, and thus the recommended dosage, infusion rates, and monitoring procedures should be adhered to. Subjects that are naïve to IGIV are more at risk than those that are well maintained and on regular therapy.

Subjects with pre-existing risk factors for thrombotic events (such as advanced age, obesity, hypertension, diabetes mellitus and a history of vascular disease or thrombotic episodes, subjects with acquired or inherited thrombophilic disorders, subjects with prolonged periods of immobilization, severely hypovolemic subjects, subjects with diseases which increase blood viscosity) may be at risk.

Subjects with DM may be at higher risk of developing thromboembolic events (TEEs). Carruthers and colleagues [33] conducted matched cohort analyses for venous thromboembolism (VTE) (i.e. deep vein thromboses [DVT] or pulmonary embolism [PE]) among individuals with PM (PM cohort) or DM (DM cohort) as compared with individuals without PM or DM (comparison cohorts), using data from the Canadian British Columbia Health Database (PopData BC). This was the first large general population-based study to assess the risk of VTE in PM/DM patients. Risk of VTE was substantially higher in individuals with PM/DM compared to the general population (six and eight times, respectively). According to Chung and colleagues [34] DM and PM patients exhibit even an 11.1-fold increased risk of VTE compared to non-DM/PM patient cohort.

Elderly patients with DM/PM exhibited a multiplicative increased risk of VTE development compared to the control panel, and the DM/PM patients with any comorbidity showed an additive risk of developing VTE.

The risk of VTE may be even higher in the initial years after diagnosis according to Carruthers and colleagues [33], PM patients had the highest risk during the first year of diagnosis and progressively attenuated over time. Similarly, DM patients had the highest risk during the first two years after diagnosis.

Therefore, special emphasis will be given to the occurrence of TEEs such as DVTs and PE.

Hemolytic transfusion reactions (HTRs) can develop subsequent to IGIV therapy. IGIV-related hemolysis is associated with passive transfer of anti-A and anti-B hemagglutinins.

When medicinal products prepared from human blood or plasma are given to a subject, the transmission of infectious agents cannot be totally excluded. This applies also to hitherto unknown pathogens. However, specific virus inactivation procedures are implemented in the manufacturing process of Octagam 10% which are described in detail in the Investigator's Brochure.

For Octagam 10%, the same type of adverse reactions has been seen as for other IGIV products. No new or unknown safety problems are expected to emerge which are not already described in the Investigator's Brochure.

As per European Federation of Neurological Societies (EFNS) Guidelines[6], IGIV is recommended as a second-line treatment in combination with prednisone in DM (level B) and treatment option in PM (level C). This is in line with the consensus statement of the American Association of Neuromuscular and Electrodiagnostic Medicine (AANEM) ad hoc committee on the use of IGIV in the treatment of neuromuscular conditions: Class I evidence exists to support the use of IGIV to treat patients with DM.[7] Over the last years, high-dose IGIV has become an effective and safe therapeutic option for DM and is beneficial as a second-line therapy for DM.[8] The European Dermatology Forum stated in their "Guideline

on the use of high-dose intravenous immunoglobulin in dermatology" that, besides Pemphigus vulgaris, DM is the dermatological condition with the highest level of evidence for treatment with IGIV. [9] IGIV is indicated for all severe forms of DM and its use as firstline treatment may be justified in patients with fulminant progressive courses, severe myolysis or paralysis. As a rule, IGIV should be used as a second-line treatment if steroid monotherapy has failed to produce an improvement after 1 month, or if reducing the steroid dose below an acceptable level results in a flare-up of the disease, or if side-effects prevent further steroid medication. The use of IGIV therapy is considered to be an adjuvant treatment with continuation of immunosuppressive therapy with corticosteroids and possibly also other immunosuppressive agents. [9.10] The German Society for Neurology also recommended in their Guideline¹ to treat patients who do not respond to corticosteroids, azathioprine or methotrexate with IGIV (Class I evidence). Similarly, the Guideline of the Therapeutics and Technology Assessment Subcommittee of the American Academy of Neurology concluded that based on one Class II study, IGIV is possibly effective for the treatment of nonresponsive DM in adults and thus may be considered for the treatment of nonresponsive DM in adults (Level C).[4,11]

Because of the ease of its application, IGIV has become the treatment of choice as corticosteroid-saving agent or as add-on therapy in severe myositis. [12]

In terms of efficacy, it can reasonably be assumed that Octagam 10% exhibits the same effectiveness as other IGIV brands.

2 STUDY OBJECTIVES

2.1 Primary Objective(s)

The primary objective of this study is to provide confirmatory data on the beneficial effect of 2.0 g/kg of Octagam 10% given every 4 weeks compared with placebo in subjects with active DM based on the percentage of responders at Week 16.

2.2 Secondary Objective(s)

The secondary objectives of this study are:

- to evaluate the beneficial effect of Octagam 10% in subjects with active DM by assessing different parameters and scores at Week 16 and Week 40;
- to confirm the sustained benefit of treatment with Octagam 10% by assessing the primary response measures at Week 40;
- to evaluate the safety and tolerability of Octagam 10% in subjects with DM.

3 INVESTIGATIONAL PLAN

3.1 Primary and Secondary Endpoints

3.1.1 Primary Endpoint

Proportion of responders in the 2.0 g/kg Octagam 10% and placebo arms at Week 16.
 A responder is defined as a subject with an increase from baseline (Week 0) of

¹ Leitlinien für Diagnostik und Therapie in der Neurologie – Myositissyndrome; www.dgn.org/leitlinien/3011-ll-69-ll-myositis-syndrome

≥20 points on the Total Improvement Score (TIS) and who has not met "Confirmed Deterioration" criteria at 2 consecutive visits as defined in Section 4.3.1 up to (including) Week 16.

3.1.2 Secondary Endpoints

Efficacy:

- Proportion of TIS responders by improvement category (minimal, moderate, major) at Week 16 and Week 40.
- Mean change from baseline (Week 0) to end of First Period (Week 16) in modified Cutaneous Dermatomyositis Disease Area and Severity Index (CDASI).[29]
- Mean change from end of First Period (Week 16) to end of Extension Period (Week 40) in modified CDASI.
- Mean change from Baseline (Week 0) to end of First Period (Week 16) and Extension Period (Week 40) in:
 - o SF-36v2 Health Survey;
 - o Individual 6 Core Set Measures (CSM) used for TIS calculation.
- Mean TIS from Baseline (Week 0) to end of First Period (Week 16) and from Baseline (Week 0) to end of Extension Period (Week 40).
- Time to minimal, moderate and major improvement in TIS.
- Time to confirmed deterioration in the First Period and overall.
- Proportion of subjects in each treatment arm who met confirmed deterioration criteria up to (including) Week 16

Safety (throughout the entire First and Extension Period):

- Occurrence of all AEs with particular emphasis on thromboembolic events (TEEs) and hemolytic transfusion reactions (HTRs).
- Occurrence of all adverse drug reactions (ADRs) and suspected ADRs.
- Vital signs (blood pressure, heart rate, body temperature and respiratory rate).
- Physical examination (at Screening and every 12 weeks from Week 4 on).
- Laboratory parameters (hematology, clinical chemistry).

Safety (at Baseline and end of Extension Period):

- Tests for viral safety.
- Pregnancy test, if applicable.

3.2 Overall Study Design and Plan

ProDERM study is planned to start in Q4 2016 and be clinically completed by Q4 2019.

ProDERM study will be a prospective, parallel group, double-blind, randomized, placebocontrolled, multicenter Phase III study in a minimum of 94 adult subjects of both genders with definite or probable DM according to the criteria of Bohan and Peter. [13,14]

As DM is a rare disease, about 55 sites are projected to participate in countries worldwide with emphasis on European countries and North America.

Subjects eligible after screening will be randomized 1:1 to receiving up to 4 infusion cycles of either Octagam 10% or placebo every 4 weeks during the First Period lasting 16 weeks. An infusion cycle comprises all infusion episodes administered over 2 (to 5) days during one visit. After response assessment at Week 16 (i.e. 4 weeks after start of the previous infusion cycle), all subjects who have not deteriorated at 2 consecutive visits during the First Period will continue to receive 2.0 g/kg (20 mL/kg) of Octagam 10% during the subsequent 6-months Extension Period. For subjects who are stable on the 2.0 g/kg (20 mL/kg) Octagam 10% dose, the investigator may decide to switch them to the 1.0 g/kg (10 mL/kg) Octagam 10% dose, starting at Week 28.

In case of confirmed deterioration (for definition see Section 4.3.1) during the First Period, subjects will be switched to the alternate treatment. After response assessment at Week 16 this subgroup of subjects will be unblinded (see Section 5.6).

Subjects originally **randomized to placebo** who did not deteriorate and thus stayed on placebo until Week 16, will all receive open-label 2.0 g/kg (20 mL/kg) Octagam 10% at Week 16. If they continue to be stable on the Octagam 10% dose, they will have the option to switch to 1.0 g/kg (10 mL/kg) Octagam 10% at Week 28, at the discretion of the investigator.

Subjects originally **randomized to placebo** and switched to Octagam 10% due to confirmed deterioration who do not further deteriorate during their Octagam 10% treatment at 2 consecutive visits will continue and receive 2.0 g/kg (20 mL/kg) Octagam 10% during the 6-months Extension Period.

Subjects originally **randomized to placebo** and switched to Octagam 10% due to deterioration, who deteriorate also during Octagam 10% treatment at 2 consecutive visits will drop-out after response assessment at Week 16 and will not enter the Extension Period.

[figure not shown]
Subjects originally **randomized to Octagam 10%** who deteriorate at 2 consecutive visits in the First Period and who were subsequently switched to placebo will drop-out after the response assessment at Week 16 and will not enter the Extension Period.

Subjects dropping out due to confirmed deterioration at 2 consecutive visits will in any case be classified as non-responders in the statistical analysis.

Any subject deteriorating at 2 consecutive visits in the Extension Period will drop-out, independent of the initially assigned treatment arm and the Octagam 10% dose administered.

Figure 1 depicts the study design.

Figure 1: Scheme of Study Design

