3.3 Discussion of Study Design and Choice of Control Group

3.3.1 Study Design

The study design of ProDERM includes all major scientific, state-of-the-art interventions needed to assess the efficacy, safety and tolerability of therapeutic treatments in DM patients.

The total observation period of the study is 40 weeks. For a proper assessment of efficacy, clinical experience has shown that at least 4 treatment cycles are necessary to be documented. This resulted in a duration of 16 weeks for the first (controlled) phase of the study. An active treatment phase of 6 months (24 weeks) is recommended by the International Myositis Assessment and Clinical Studies Group.[32]

In order to minimize the risk for subjects in the **placebo arm**, a conditional switch to active treatment is introduced in the (blinded) First Period: All subjects in the placebo arm who deteriorate at 2 consecutive visits until Week 8 or after Week 8 will be switched to 2.0 g/kg (20 mL/kg) of Octagam 10%. In case of further, confirmed deterioration on the Octagam 10% treatment, subjects will drop-out.

In contrast, subjects in the 2.0 g/kg (20 mL/kg) **Octagam 10% arm** will receive placebo if they deteriorate at 2 consecutive visits until Week 8 or after Week 8. In case of confirmed deterioration after the switch to placebo, subjects will eventually drop-out. Subjects who did not deteriorate after the switch to placebo at 2 consecutive visits will automatically drop out at Week 16. This procedure was introduced to maintain the blinding of treatment.

In the Extension Period of the study, subjects will receive 6 infusion cycles of 2.0 g/kg (20 mL/kg) of Octagam 10% every 4 weeks. If the subject is stable on the 2.0 g/kg (20 mL/kg) dose, the investigator may decide on a case by case basis, if they want to treat the subject with the lower dose of 1.0 g/kg (10 mL/kg) Octagam 10%, starting at Week 28. Thereby, data on long-term efficacy and tolerability will be generated.

The 4-week interval between infusions has been chosen to make results comparable to the old Dalakas study [4] and to stay in line with current clinical practice.

Immunosuppressive agents and corticosteroids are allowed if stable dosages are not exceeded (see Section 4.2.1) in order to comply with the EFNS Guidelines saying that IGIV is recommended as a second-line treatment. [6]

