4.3 Withdrawal and Replacement of Subjects

4.3.1 Premature Subject Withdrawal

Subjects have the right to withdraw from the study at any time for any reason, without the need to justify their decision. The Investigator also has the right to withdraw subjects from the study in case of AEs, poor compliance, or other reasons. Since an excessive rate of withdrawal can render the study non-interpretable, the unnecessary withdrawal of subjects must be avoided.

For any discontinuation after study entry, the Investigator will obtain all the required details and document the reason(s) for discontinuation in the eCRF. If the reason for withdrawal of a subject is an AE, the main specific event or laboratory test will be recorded in the eCRF, and the Investigator will make thorough efforts to clearly document the outcome.

Should a subject decide to withdraw, the Investigator will make the best efforts to complete and report the observations. The Investigator will document the reason(s) for withdrawal of each subject in the eCRF.

Subjects who terminate the study prematurely are drop-outs. The Investigator has to organize the Drop-out visit which is identical to the Termination visit procedures.

At Week 16, certain subjects have to drop-out, especially in case of (further) confirmed deterioration after the switch to the alternate treatment option. Please see Figure 1 for details.

Other reasons for premature termination of subjects may be:

- 1. Withdrawal of subject's consent.
- 2. Deterioration of DM (during Extension Period).
- 3. Pregnant subjects will be immediately excluded from the study.

- Investigator's opinion that the subject may be severely harmed if he/she continues trial participation, namely by the treatment and procedures according to the study protocol.
- 5. Occurrence of a disease which interferes with the study treatment or represents an exclusion criterion.
- 6. Administration of IGIV other than Octagam 10%.

"Confirmed deterioration" is essentially defined as follows according to Oddis et al. 2013 with a slight adaptation as agreed with the study's Steering Committee (excluding enzymes, which will not immediately be available for the evaluation of deterioration): [20]

• Physician's Global Disease Activity VAS worsening ≥ 2 cm and MMT-8 worsening ≥ 20% on 2 consecutive visits,

or

• global extra-muscular activity worsening ≥2 cm on the MDAAT VAS on 2 consecutive visits,

or

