• any 3 of 5 CSM (excluding enzymes) worsening by ≥30% on 2 consecutive visits.

For all criteria worsening will be determined by comparing to baseline (Week 0) values.

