4.1. Overall Study Design and Plan

Study GAM10-08 is designed as a prospective, parallel group, double-blind, randomized, multicenter phase III study with a 16-week efficacy period followed by a 24-week open-label extension period.

As DM is a rare disease, about 55 sites are projected to participate in countries worldwide with emphasis on (Eastern) European countries and North America. For the same reason, it is not expected that single centers will enroll more than about 5 subjects.

The duration of the entire study for each subject will be up to 43 weeks and consists of the following segments:

- approximately 3 weeks for Screening
- 16 weeks of double-blind treatment
- 24 weeks of open-label treatment with Octagam

[figure not shown]
Eligible subjects after screening will be randomized 1:1 to receive up to four infusion cycles of either 2.0 g/kg Octagam 10% or placebo every 4 weeks during the 16-week First Period. An infusion cycle will consist of 2 to 5 days over which the study drug will be administered.

Subjects, who deteriorate³ in this phase, will be crossed-over to the alternate treatment from week 8 on.

After response assessment at Week 16, the following subject groups will continue in the 6-months open-label Extension Period and receive 2.0 g/kg Octagam 10% given over 2 days (if tolerated by the patient) at 4 week intervals:

- Subjects randomized to Octagam without confirmed deterioration during the First study period including Week 16.
- Subjects randomized to placebo without confirmed deterioration prior to Week 16.
- Subjects randomized to placebo who switched to Octagam and show no further deterioration at Week 16

The rest of the subjects will not continue the study, but Week 16 will be considered as their termination visit:

³ For a definition of confirmed deterioration, please refer to section 8.4.

At Week 28, subjects who are stable on 2.0 g/kg Octagam 10% can be switched to 1.0 g/kg Octagam 10%, at the discretion of the investigator.

Please refer to the study protocol for a detailed flowchart of planned study events and assessments.

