5.1. Final Analyses and Reporting

As stated in section 4.1, this study consists of a double-blinded period, followed by an open-label extension period. The blind will however be maintained throughout the complete study to the extent possible; only for subjects who were switched during the first study period and show no further deterioration at Week 16 and for those subjects with confirmed deterioration at Week 16, the decision whether a subject is allowed to continue into the open-label period will imply whether the subject was initially treated with Octagam (Subject has to drop out) or Placebo (Subject continues). Otherwise the blind will not be broken before all subjects have completed the entire study and the final database has been locked and released for analysis according to the applicable standard operating procedures.

This process includes a data review, the identification and classification of any protocol deviations as detailed in section 7, and thus the subject disposition with respect to the analysis populations. All final, planned analyses identified in the protocol and in this SAP will be performed only after the last subject has completed the study, the subject disposition has been agreed and documented, and the final SAP has been approved.

Key statistics and study results will be made available to the study team following database lock and prior to completion of the final CSR by means of tables, figures and listings.

Any, post-hoc, exploratory analyses completed to support planned study analyses, which were not identified in the final SAP, will be documented and reported in the CSR or its appendices. Any results from such unplanned analyses will also be clearly identified in the text of the CSR.

No interim analysis is planned.

6. Sample Size Determination

The sample size calculation is based on the target parameters for the evaluation of the primary endpoint, i.e. the proportions of responders in the Octagam 10% and the placebo group at the end of the 16 week efficacy period (First Period).

A total sample size of 84 subjects is required to show a significant difference in the proportion of responders between Octagam and placebo group with a power of 80%, under the assumption that the true proportions of responders are 0.6 in the Octagam group and 0.3 in the placebo group. The sample size calculation is based on Pearson's chi square test using a two-sided alpha level of 0.05.

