8.4. Derived and Computed Variables

The following derived and computed variables have been initially identified as important for the analysis of the primary and secondary target variables. It is expected that additional variables will be required. The SAP will not be amended for additional variables that are not related to the primary target or key secondary target variables. Any additional derived or computed variables will be identified and documented in the SAS programs that create the analysis files. If the SAP is not amended, further derivations related to primary and secondary target variables will be described in the CSR.

- **Age** will be derived according to the usual definition that a person is n years old until she or he has completed her or his $(n+1)^{\text{th}}$ year of life, using the date of informed consent as the reference date. This is also the definition that will be applied for evaluation of the age related inclusion criteria. [Unit: years]
- **Body Mass Index:** $\text{BMI} = (\text{Body weight}) / \text{Height}^2$ [Unit: kg/m^2]
- The **treatment period** is defined as the period between the day of first treatment with study drug (Octagam or placebo) to the end of the observation period. This will usually be the termination visit.
- **Confirmed Deterioration** is defined as follows:
 - Physician's Global Disease Activity VAS worsening $\geq 2\text{cm}$ and MMT-8 worsening $\geq 20\%$ on 2 consecutive visits,
 - or
 - global extra-muscular activity worsening $\geq 2\text{cm}$ on the MDAAT VAS on 2 consecutive visits,
 - or
 - any 3 of 5 CSM (excluding enzymes) worsening by $\geq 30\%$ on 2 consecutive visits.

For all criteria worsening will be determined by comparing to baseline values (Week 0).

9. Study Subjects and Demographics

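### After a switch from placebo, deterioration on Octagam is still measured from Week 0, so a patient improving since the switch can be dropped and counted as deteriorating on Octagam

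*Protocol*

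**What the plan says.** **Continuation rule, protocol.** Section 3.2 says that placebo patients switched to Octagam "who deteriorate also during Octagam 10% treatment at 2 consecutive visits will drop-out after response assessment at Week 16". The counterpart rule is that those "who do not further deteriorate during their Octagam 10% treatment at 2 consecutive visits will continue" into the Extension Period. Section 3.3.1 puts it as: "In case of further, confirmed deterioration on the Octagam 10% treatment, subjects will drop-out".

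**Continuation rule, SAP.** Section 4.1 lists among those who continue: "Subjects randomized to placebo who switched to Octagam and show no further deterioration at Week 16". Section 5.1, on unblinding, uses the same phrase: "only for subjects who were switched during the first study period and show no further deterioration at Week 16".

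**Reference value.** Protocol 4.3.1 defines confirmed deterioration by three alternative criteria, each required at two visits in a row, and adds: "For all criteria worsening will be determined by comparing to baseline (Week 0) values". SAP 8.4 repeats the criteria and also fixes the comparison at Week 0. Neither text says what *further* means or resets the reference at the switch.

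**Where it enters the analysis.** Protocol 9.2.2 and SAP 10.2 extend the Kaplan-Meier analyses, including time to confirmed deterioration, into the Extension Period by relating events to the first Octagam infusion. Week 40 response rates and changes are summarised descriptively.

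**The concern.** The words *further* and *during* suggest a question about what happened after Octagam was started. The definition answers a different one: whether the patient is still worse than at Week 0. A placebo patient is switched only after crossing the Week 0 threshold twice, so begins Octagam already above it. Partial recovery that has not yet fallen below the threshold cannot be told apart from deterioration on Octagam.

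Slow or partial recovery is plausible on the protocol's own account. Section 7.5 reports that most responders in the earlier controlled IGIV trial responded after the second course, and section 3.3.1 holds that at least four cycles are needed for a proper assessment. A Week 8 switcher has had one Octagam cycle when assessed at Week 12 and two at Week 16.

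The second difficulty is the number of visits. The protocol asks for two during Octagam treatment. The SAP names only Week 16, and a Week 12 switcher has no other scheduled assessment on Octagam.

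At stake are entry to the Extension Period, the Week 40 summaries, and the attribution of deterioration in the analysis timed from first Octagam infusion.

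**Working it through.** **1. The plan's sample size, for orientation.** Protocol 9.1 assumes 0.6 against 0.3, two-sided alpha 0.05 and 80% power by Pearson's chi-square. With pooled proportion 0.45, n per arm = [1.960 × √(2 × 0.45 × 0.55) + 0.842 × √(0.24 + 0.21)]² / 0.3² = 41.97, hence 42 per arm and 84 in total, as stated. Nothing below depends on this figure.

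**2. Visits on Octagam.** Core set measures are taken before infusion at Weeks 4, 8 and 12 and again at Week 16 (Protocol 6.1.3 to 6.1.5). Two consecutive deteriorated visits put the switch at Week 8 or Week 12.
- Switch at Week 8: scheduled assessments on Octagam at Weeks 12 and 16, so two.
- Switch at Week 12: one, at Week 16. The Week 12 assessment precedes the first Octagam infusion and reflects placebo.

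**3. An improving Week 8 switcher (hypothetical values).** The criterion is "global extra-muscular activity worsening ≥2 cm on the MDAAT VAS on 2 consecutive visits".

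| Week | Extra-muscular VAS (cm) | Change from Week 0 | Change from switch |
|---|---|---|---|
| 0 | 3.0 | – | – |
| 4 | 6.5 | +3.5 | – |
| 8 (switch) | 6.5 | +3.5 | 0 |
| 12 | 5.5 | +2.5 | −1.0 |
| 16 | 5.0 | +2.0 | −1.5 |

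The criterion is met at Weeks 12 and 16, both on Octagam, although the patient improves at each visit after the switch. Measured from Week 8 it is not met.

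The criterion pairing physician VAS with MMT-8 can behave the same way. Take physician VAS 4, 8.5, 7.5 and 6.5 cm and MMT-8 130, 90, 97 and 103 at Weeks 0, 8, 12 and 16.
- Week 12: +3.5 cm and (130 − 97)/130 = 25.4% worse.
- Week 16: +2.5 cm and (130 − 103)/130 = 20.8% worse.

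Both visits meet the criterion, while from Week 8 to Week 16 the physician VAS falls by 2.0 cm and MMT-8 rises by 13 points.

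**4. All switch patterns.** Write 1 where the criteria are met against Week 0, in the order Weeks 4, 8, 12, 16. Six patterns trigger a switch.

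| Pattern | Switch | Protocol, visits on Octagam only | SAP, Week 16 alone | Two-visit rule counting Weeks 12 and 16 |
|---|---|---|---|---|
| 1100 | Week 8 | continue | continue | continue |
| 1110 | Week 8 | continue | continue | continue |
| 1101 | Week 8 | continue | drop | continue |
| 1111 | Week 8 | drop | drop | drop |
| 0110 | Week 12 | continue | continue | continue |
| 0111 | Week 12 | continue | drop | drop |

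The improving patient in step 3 is pattern 1111 and is dropped on every reading. If the SAP phrase means confirmed deterioration (section 8.4), 1101 is no longer in conflict. Pattern 0111 then turns on whether the pre-infusion Week 12 visit counts.

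**The case against.** The strongest reply is that the text is more coherent than it looks. Week 0 is explicit and common to both documents. In SAP 4.1 the crossover sentence carries a footnote to section 8.4, where every criterion needs two visits, so *at Week 16* may only mark when the decision is taken. Sites follow the protocol, whose literal wording has a Week 12 switcher continue. Protocol 4.3.1 and 5.6 also send the reader to Figure 1, which was not available and may show which visits count.

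Much of this stands, and it rules out several stronger readings:
- *The two documents use different reference values.* They do not; both use Week 0.
- *The SAP plainly contradicts the protocol on the number of visits.* The footnote permits a two-visit reading, which leaves only pattern 0111 open. The openness is real, because the two neighbouring items in the SAP 4.1 list say confirmed deterioration and this one does not.
- *The primary result is biased.* Switched patients are already non-responders in their randomised group (SAP 4.3 and 10.1), and by-visit tables exclude values after a First Period switch (SAP 7).
- *All switchers are affected, some 5 to 12 patients.* Assuming that 10 to 25% of 94/2 = 47 placebo patients switch gives 4.7 to 11.75. The documents give no switch rate, and this counts every switcher, not only those who have partly recovered but remain above the threshold.

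Whether a patient still well above the Week 0 value should continue is a clinical question, and a Week 0 reference is not an error in itself. The reply does not remove the attribution problem: the stated definition, followed as written, records worsening that arose on placebo as deterioration during Octagam. An unscheduled visit (Protocol 6.1.9) could add an assessment for a Week 12 switcher, but it is not required and nothing says it counts.

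**Conclusion.** The point holds in a limited form. With Week 0 as the reference for all criteria, a Week 8 switcher who has improved since the switch but remains above the threshold at Weeks 12 and 16 meets confirmed deterioration on Octagam and leaves before the Extension Period. The same patient can be an event in the Kaplan-Meier analysis timed from first Octagam infusion; this assumes that the SAP 8.4 definition is applied there unchanged, since no other is given. For a Week 12 switcher who is also worse at Week 16, the outcome depends on whether the pre-infusion Week 12 visit counts.

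The effect is confined to Extension entry, the descriptive Week 40 summaries and the analyses that follow patients from first Octagam infusion. The primary endpoint, sample size and power do not change. The number of patients affected cannot be derived from the documents and is only a subset of switchers. Figure 1 might settle which visits count.

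**What to change.** **In the SAP (10.2, with a derivation in 8.4).** For switched patients, and for the analyses timed from first Octagam infusion, derive and report separately: (i) still worse than Week 0 by the criteria but improved since the switch, and (ii) worse than at the switch. State how patients unchanged since the switch are shown. Worsening that arose on placebo is then not attributed to Octagam.

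**In both documents.** Reconcile Protocol 3.2, 3.3.1 and 4.3.1 with SAP 4.1, 5.1 and 8.4 on the reference value for further deterioration, the number of visits required, and which visits count for Week 8 and Week 12 switchers, and check the result against Figure 1. The choice of continuation rule is for the sponsor's clinical team; none is proposed here.

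**Cost.** One small derivation and one table from core set measures already collected, plus a wording clarification. No new visits, and no change to the primary analysis.
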